6.1.2 ADMINISTRATION AND/OR DOSING

Please see section 6.1.1.

6.2 FIDELITY

6.2.1 INTERVENTIONIST TRAINING AND TRACKING

Specific to the intervention the table below identifies the frequency of monitoring intervention fidelity:

Data source	Monitoring frequency	Area of fidelity	
		Study design	Treatment delivery
Personal training checklist	Weekly	x	x
Review of two-way messaging	2 to 4 days	x	x
Team meetings to discuss participant progress and protocol adherence	Weekly	x	

Additionally, prior to commencing the study, research staff will undergo training on how to maintain consistency when communicating via Companion and during outcome measurement. Communication training will be based on guidelines for motivational interviewing. After training on outcome measurement, a skill test will be conducted on a test individual by research staff to determine inter-tester agreement.

6.3 MEASURES TO MINIMIZE BIAS: RANDOMIZATION AND BLINDING

1:1 Simple Randomization conducted by graduate assistant.

It has been suggested that blinding in behavioral interventions such as those involving physical activity and exercise is comparatively more challenging than in pharmacological or medical studies; this may be more relevant to pilot trials that are not conducted as part of a larger trial, which aim to assess the conceivable benefits of an intervention and the potential of conducting a future definitive RCT.⁷⁻⁹ While the health coaches and participants will not be blinded to treatment allocation, we minimize bias via the use of objectively measured outcome variables in both aims. Furthermore, the statistical analyst will be blinded to treatment allocation during analyses.

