1 PROTOCOL SUMMARY

1.1 SYNOPSIS

Title:	An Integrated Two-Way Communication and Near-Real-Time Sensing System to Detect and Modify Daily Inactivity among Adults Over Age 60
Grant Number:	5P30AG048785-07
Study Description:	The objective is to test if Companion, an Integrated Two-Way Communication and Near-Real-Time Sensing System, improves and sustains overall daily free-living activity and sedentary behavior in adults over 60 y. The central hypothesis is that Companion will improve overall daily free-living activity and sedentary behavior in adults >60 y and thereby improve their health.
Objectives*:	
Primary Objective: Determine if Companion improves free-living activity and sedentary behavior and sustains this change in adults >60y. In this RCT (n=46), both treatment and control groups will engage in a 16-week supervised exercise program and then be followed-up after 24 weeks.^{1,2} Companion will be deployed in the treatment group (n=23) only. Primary outcomes are daily total and bouts of physical activity and sedentary time.
 
Exploratory Objective: Explore if supplementing supervised exercise with Companion further improves and sustains cardiometabolic health, body composition, cognition, and psychosocial outcomes.

Endpoints*:	
Primary Endpoint: Physical activity and sedentary time: Daily total and bouts
 
Exploratory Endpoints: Anthropometrics; Plasma glucose; HbA1C; Insulin; Lipids; Lean and fat mass; Physical function; Muscular and aerobic fitness; Cognition; perceptions of competence related to health behavior; Autonomy support (from companion); Autonomous motivation (for physical activity); Relatedness (to the Companion); General satisfaction.

Study Population:	N= 46, gender- NA, age >60 y, demographic group- older adults; general health status- healthy; geographic location- Boston and surrounding neighborhoods.
Phase* or Stage:	1A
Description of Sites/Facilities Enrolling Participants:	The Human Performance and Exercise Science (HPES) Laboratory is located in the Behrakis Health Science Center at Northeastern University, which will be the sole site for the study. Participants who do not prefer to have their measurements conducted at their residence will come to the lab to have measurements completed. The study is not intended to include sites outside of the United States.

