4 STUDY DESIGN

4.1 OVERALL DESIGN

Hypothesis (Aim 1): The treatment group will show greater improvements in daily activity and sedentary behavior outcomes than controls after 16 and 24 weeks.

Hypothesis (Aim 2): The treatment group will show greater improvements in health and psychosocial outcomes than controls after 16 and 24 weeks.

Phase: 1A.

Design: Randomized control trial

Participant assignment: 1:1 Simple Randomization conducted by graduate assistant

Number of study group: 2 (control/treatment); intervention period= 4 months; follow-ups after 4 and 6 months.

Number of sites= Single site trial.

Name and description of intervention: Companion; An integrated system of wearable sensors and the smartphone. It is a behavior-aware, virtual “Companion” that uses a “human-in-the-loop” approach to enable meaningful two-way communication. Companion builds rich models of typical behavior using sensors and context sensitive ecological momentary assessment (CS-EMA) to deliver intervention components and behavior change strategies using socially engaging, contextually salient, and tailored text-message conversations in near-real-time.

Description of control group: This group will not receive the Companion, which will be the only difference with the treatment group. I.e., the control group will receive standard treatment– the supervised training program and an exercise prescription for those days without supervision.

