Supervised Exercise Program: For the first 16 weeks, all participants will engage in ~45 to 60 min of aerobic, strength, flexibility and balance training, twice/week.^{29,35} Participants will either visit Northeastern's Exercise Science Lab for supervised personal training or engage virtually over Zoom during the training session. The lead trainers will be an exercise physiologist or a trained graduate student. After the session, the trainer and participant will outline goals and prescription plan for the days prior the next training session and those to be performed by the participant on their own. The plan

will be based on guidelines from the American College of Sports Medicine.^{36,37} Supervised training sessions for the two groups will be scheduled on different days and allocation of participants to a trainer will be at random.

Treatment Group: This group will receive the Companion. Communication during weeks 1 to 4, will focus on gathering information on the participant's motivations, preferences, habits, contexts, and usual behavior patterns to build a typical behavior model for the participant. We expect a decreasing level of change in behavior models that are built using information accrued incrementally over these 4 weeks.²³ Companion will monitor ongoing and recent behavior, communicate with the participant (if necessary) to deliver contextually salient intervention strategies. Additionally, there will be a fixed Companion-initiated communication in the early evening (~4 to 6 pm) to discuss the achievement of that day's goals and prescribe strategies to achieve pending goals.

The nature of the first communication the next morning will be based on participant performance during all waking hours of the preceding day- e.g., encouraging, problem-solving. This is possible because the participant will be instructed to continuously wear the wrist device, which stores motion data in its internal memory. These data will be downloaded to Companion and analyzed.

Regular interaction will enable a corresponding incremental personalization of communication based on knowledge of each participant's communication style and personality. Similarly, such frequent interaction will also enable an incremental knowledge of the participant's changing physical ability and activity preferences, which will facilitate a corresponding increase in personalizing activity prescription.

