9.2 SAMPLE SIZE DETERMINATION

Sample size is based on change in HbA1C after 16 weeks of training in adults >60 y (n=22). We used a health outcome variable to compute sample size to examine the translational effect of behavior change due to Companion on the health of adults >60 y. In our data, partial η^2 (effect size) for the interaction effect between group and time (pre – 16 week) equaled 0.5 corresponding to a medium effect size. With alpha of .01, power of 0.85, two groups, 3 repeated assessments, and an estimated inter-correlation between assessments of 0.5, the required sample is 39; we will recruit 46 participants. Hypothesis testing for all outcomes will entail an intent-to-treat two-tailed design with a type I error of 0.05.

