10.1.1.2 CONSENT PROCEDURES AND DOCUMENTATION

The project manager and/or graduate student trained in the consent process will obtain informed consent and potential participants will receive an oral explanation regarding study procedures and associated risks and benefits. Participants will be made aware that their participation is voluntary, and they have the right to stop participation at any time. Risks associated with the study will be clearly outlined in the informed consent document. Participants will have time to read the consent form and the experimenter will address participants' questions and concerns prior to signing the consent form. The participant will be explicitly told that they can take as long as needed to read over and ask questions. We will ensure confidentiality during the consent process and allow participants sufficient time to make a decision on participation. Signed consent will be obtained prior to admission to the study. This will include a complete description of the study and will include telephone numbers to contact the principal investigator and Institutional Review Board (IRB) if they have questions.

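### Simple 1:1 randomisation of 46 seldom gives the stated 23 in the Companion arm, and randomising on Day 1 lets assignment be known before baseline activity is measured

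*Combined protocol and SAP*

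**What the plan says.** Section 4.1 (Overall Design) states: "Participant assignment: 1:1 Simple Randomization conducted by graduate assistant". Section 6.3 repeats it: "1:1 Simple Randomization conducted by graduate assistant". These are the only descriptions of the allocation method. Neither mentions blocks, strata, how the sequence is generated, or who holds it.

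The synopsis (1.1) gives a total of 46 and says "Companion will be deployed in the treatment group (n=23) only". Section 9.2 gives the source of the total: "the required sample is 39; we will recruit 46 participants".

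On blinding, Section 6.3 says "While the health coaches and participants will not be blinded to treatment allocation". The protections it names are objective outcomes and a blinded analyst.

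On timing, the schedule in Section 1.3 puts consent, outcome evaluation and randomisation all at Measurement 1, Day 1. Section 8.1 hands out the activity monitors after the Table 1 tests, and the thigh monitor is then worn for 7 days as the baseline. Section 8.2 links the taped sensor to the primary outcome. Section 8.1 also gives the two groups different wrist devices, worn throughout the study including the baseline week. In the lifestyle group, which I read as the Companion arm, a data hub is installed at the start.

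**The concern.** Two things do not fit together.

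First, the synopsis gives a fixed size for the Companion arm, while the named method leaves that size to chance. If 23 per arm is meant as a property of the design, simple randomisation does not provide it. The consequences are some loss of precision and uneven demand on coaches and on training sessions, which Section 6.1.1 schedules on different days for the two groups.

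Second, if assignment is made on Day 1 and the baseline week follows, participants and coaches can know the arm while baseline activity is being recorded. Even if staff announce nothing, the wrist device and the hub show the arm. A participant who knows that coaching is coming may move more, or less, during that week. Sections 9.4.1 and 9.4.2 use the baseline value as an adjustment where necessary, and Section 9.4.5 compares the arms at baseline. Both assume a baseline unaffected by assignment.

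**Working it through.** **Inputs.** N = 46 (1.1, 9.2); Companion arm 23 (1.1); each person assigned independently with probability 0.5 (4.1, 6.3, taking simple in its usual sense).

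**The plan's figure.** 46 × 0.5 = 23. This reproduces the stated arm size, but as an expected value.

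**Distribution of the arm size.** The size X follows Binomial(46, 0.5).

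- P(X = 23) = C(46, 23) / 2^46 = 0.117, so the stated split is missed with probability 0.883.
- P(27/19 or more uneven, gap ≥ 8) = 0.302.
- P(28/18 or more uneven, gap ≥ 10) = 0.184.
- P(29/17 or more uneven, gap ≥ 12) = 0.104.
- The mean absolute gap is 5.4 people. The central 95% range for one arm is 16 to 30.

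**Precision.** Effective N = 4·n1·n2 / 46.

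- 18/28: 4 × 18 × 28 / 46 = 43.8, a loss of 4.7%; the standard error rises by √(23² / (18 × 28)) − 1 = 2.5%.
- 17/29: 4 × 17 × 29 / 46 = 42.9, a loss of 6.8%.
- Average: E[X(46 − X)] = 46 × 45 / 4, so mean effective N = 45.0, a loss of 1/46 = 2.2%.

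**Power, for illustration.** Take a two-sample t-test at two-sided 0.05, with the effect set to give 85% power at 23/23. Power is 83.3% at 18/28, 81.4% at 16/30, and 84.2% averaged over all splits. The average loss is under one percentage point.

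**Covariate balance.** The chance that a standardised baseline difference exceeds 0.5 in either direction depends on √(1/n1 + 1/n2). At 23/23 this is 0.295, which gives 9.0%. At 18/28 it is 0.302, which gives 9.8%.

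**What blocks would do.**

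- Randomly chosen blocks of 2 and 4 cut off at 46 give 23/23 about 89% of the time (simulation), and otherwise 24/22. Blocks of 4 and 6 cut off at 46 give it about 78% of the time. Only a list built to total 46 gives 23/23 by construction. Four blocks of 4 and five of 6, in random order, do so: 16 + 30 = 46.
- Predictability: suppose someone sees all past assignments and always guesses the arm that is behind. A block of 2m then yields on average m + (4^m / C(2m, m) − 1) / 2 correct guesses: 1.5 of 2, 2.83 of 4, 4.1 of 6. An equal mix of 2s and 4s gives (1.5 + 2.83) / 6 = 72%. The list of four 4s and five 6s gives (4 × 2.83 + 5 × 4.1) / 46 = 69%. Simple randomisation gives 50%.
- Someone who also knows the block size can predict with certainty 50%, 33% or 25% of assignments for blocks of 2, 4 or 6.

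**Timing.** Side by side: randomisation on Day 1 (1.3); monitors handed out after the Day 1 tests and worn for 7 days (8.1); counselling that differs by arm at Day 7–14 (1.3, 8.1). Nothing in the schedule requires assignment before the counselling visit, apart from the arm-specific devices and hub and any training session booked by arm before that visit. If the 16 weeks (112 days) run from that visit, they end at Day 119–126, close to the Day 120–130 window for Measurement 2.

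**The case against.** The case for leaving the method alone is reasonable. Simple randomisation is valid and unbiased, and it is the least predictable method, which is worth something in an open single-site trial. The figure of 23 may be only a target, or simple may have been used loosely for a shuffled list of 46. The average information loss is 2.2%, and covariate adjustment is already planned. All of this stands. It makes the arm-size point an improvement and not a defect in validity.

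Blocks also have a price. As shown above, small blocks can be guessed well by anyone who sees past assignments, and concealment limits this without removing it. Moving the reveal is more than a wording change, because devices and the hub differ by arm.

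Three stronger readings are tempting, and the documents do not support them.

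- **Overlapping roles.** A reader might infer that one person randomises, consents and trains. Section 10.1.1.2 says "The project manager and/or graduate student trained in the consent process will obtain informed consent", Section 6.1.1 says "The lead trainers will be an exercise physiologist or a trained graduate student", and a graduate assistant randomises. Nothing says these are the same person, and Section 10.1.5 (Key Roles and Study Governance) was not in the text available for this review.
- **No concealment.** The available text does not describe it. That is a gap in description and does not show that concealment is absent in practice.
- **Better covariate balance.** Unstratified blocks balance numbers over time, not specific covariates. The change from 9.0% to 9.8% shows how little arm size matters here.

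**Conclusion.** The point holds as a cheap improvement in two parts.

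The stated 23 in the Companion arm is reached exactly only 11.7% of the time under the named method, with a gap of 10 or more 18.4% of the time. The statistical cost is modest: effective N averages 45.0 of 46, and about 5% of information is lost at 18/28. This assumes that simple means independent equal-probability assignment and that exactly 46 are randomised. The replacement rule in Section 7.2 could move the final numbers further.

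The order of events in Sections 1.3 and 8.1 permits the baseline of the primary outcome to be recorded after assignment is known. The documents give no basis for the size or direction of any resulting bias. The point rests on the schedule as written; site practice may differ.

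**What to change.** **Sections 4.1 and 6.3.** Replace simple randomisation with a computer-generated permuted-block list that totals 46. Block sizes should vary at random, stay undisclosed, and preferably exceed 2: for example 4 and 6, with the last block sized so that the list totals 46, or the four 4s and five 6s shown above. State that existing staff who do not consent, train or coach hold the list and release one assignment at a time. Say also how a replacement under Section 7.2 is assigned, for instance by the next place on an extended list.

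**Section 1.3.** Move randomisation to after the 7-day baseline wear, at or just before the Day 7–14 virtual visit and before the counselling that differs by arm.

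**Section 8.1.** Issue arm-specific wrist devices only after randomisation, or use the same device in both arms during the baseline week. Install the hub after randomisation as well.

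**Cost.** A few sentences, a pre-generated list, and a small change to the schedule and device hand-out; no extra participants. Any supervised session now booked by arm during the first week would have to wait for assignment. The remaining downside is somewhat greater predictability than under simple randomisation, limited by concealment and varying block sizes. If the investigators keep simple randomisation, they should label 23 as an expected number and still describe concealment and move the timing.

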5. **Cognitive tests:** The participant will complete a computer-administered test that measures various aspects of his or her cognitive abilities (attention, mental skills, memory, and processing speed).
6. **Physical function tasks:** The participants' pattern of walking (Gait), endurance, strength and balance will be evaluated by a series of performance assessments, which are safe and practical. These assessments mimic daily activities. Details of these performance assessments are as follows:
 - (i) **Gait:** the participant will be asked to walk at his or her usual pace on a 4-meter course twice. The researchers will time each of these walks with a stopwatch.
 - (ii) **Endurance:** the participant will first be asked to perform a series of chair stands. Beginning from a sitting position, the participant will be asked to stand up and then sit down five times in a row, as fast as he or she can, without using his or her arms to help.
 - (iii) **Strength:** the participant will be asked to squeeze a hand-held device to determine the maximum force he or she can produce with each hand repeating the test three times for the left and right hands.
 - (iv) **Balance:** the participant will first be asked to stand in different positions while keeping his or her balance first with eyes open and then with eyes closed. The tester will demonstrate what to do and will be nearby to steady the participant if he or she needs it.
7. **Muscular and Aerobic Fitness:** We will assess the participant's fitness with a series of short assessments explained below. A trained exercise physiologist will spot and supervise all exercises to ensure safety and proper technique. All testing procedures will be preceded with proper warm-up and instructions to minimize any risks. Details of these assessments are as follows:
 - (i) **Muscular endurance:** We will assess the endurance of the participant's lower and upper body by asking he or she to perform as many repetitions as possible. For the upper body we will do the Standard Push Up test where participants will perform as many pushups as possible. For the lower body we will use the Repetitive Squat Test where the participant stands with feet 15 cm apart, squats

until the thighs are parallel to the floor, and returns to an upright position. We will record the number of repetitions. The participant is free to terminate the tests at any moment either upon voluntary exhaustion or lack of desire to continue.

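### Section 6.3 relies on objective outcomes in both aims, but about half of the listed Aim 2 endpoints are self-reported, hand-timed or effort-dependent, and assessor blinding is not addressed

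*Combined protocol and SAP*

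**What the plan says.** Section 6.3 concedes that health coaches and participants know the allocation. It offers two protections: "we minimize bias via the use of objectively measured outcome variables in both aims", and that "the statistical analyst will be blinded to treatment allocation during analyses". Outcome assessors are not mentioned there or elsewhere.

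Section 4.1 states the Aim 2 hypothesis: "The treatment group will show greater improvements in health and psychosocial outcomes than controls after 16 and 24 weeks". The synopsis lists the psychosocial part as "perceptions of competence related to health behavior; Autonomy support (from companion); Autonomous motivation (for physical activity); Relatedness (to the Companion); General satisfaction". Section 8.1 (Table 2 and the text below it) measures these constructs with self-completed questionnaires.

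For the 4-metre gait test, section 8.1 says: "The researchers will time each of these walks with a stopwatch". Chair stands are done as fast as possible, grip strength is a maximal squeeze, push-ups and squats continue until the participant chooses to stop, and aerobic fitness is the distance walked in 6 minutes.

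On staffing, section 6.2.1 says that "research staff will undergo training on how to maintain consistency when communicating via Companion and during outcome measurement". Section 6.1.1 says: "The lead trainers will be an exercise physiologist or a trained graduate student". Section 8.1 says of the fitness tests: "A trained exercise physiologist will spot and supervise all exercises to ensure safety and proper technique".

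**The concern.** Objective measurement is the only protection in 6.3 that acts at the point where data are recorded. Blinding the analyst cannot remove a bias that is already in the data. If the objectivity claim fails for an endpoint, that endpoint has no stated protection in an open-label comparison.

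Two routes are open. A tester who knows the arm can start or stop a watch, count a borderline repetition or encourage effort differently. A participant who knows the arm can try harder or answer more favourably. The first route matters most if the tester is also that participant's Companion coach, because coaching exists in one arm only.

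At stake is what Aim 2 can conclude about function, fitness and psychosocial outcomes. Section 9.4.9 plans effect sizes and confidence intervals for all these comparisons, and 6.3 itself describes pilot trials as a step towards a future definitive trial. A reader of 6.3 would take those effect sizes as better protected than they are.

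**Working it through.** The plan gives no figure to reproduce here. The check is a classification of endpoints, a reading of who does what, and an illustration of size.

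**1. Classification of the 14 exploratory endpoints in the synopsis**

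- Instrument-read (6): anthropometrics, plasma glucose, HbA1c, insulin, lipids, lean and fat mass. Anthropometrics are counted here although the circumferences are taken by hand with a tape, in triplicate.
- Hand-timed or effort-dependent (3): physical function, muscular and aerobic fitness, cognition.
- Self-reported (5): competence, autonomy support, autonomous motivation, relatedness, general satisfaction.

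Share not objectively measured: (3 + 5)/14 = 8/14 = 57%. The cognitive test is computer-administered, so scoring is automatic even though effort is not. Counting it as objective gives 7/14 = 50%. The shorter list in section 3 gives 7/12 = 58%, or 6/12 = 50% on the same alternative. About half is therefore a fair description. The five self-reported endpoints alone are enough to contradict the words about both aims.

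**2. Who measures and who intervenes**

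- Section 6.2.1: one group, research staff, is trained for Companion communication and for outcome measurement.
- Section 8.1: the same term, the researchers, is used for those who time the gait test and for those who send the text-message feedback.
- Sections 6.1.1 and 8.1: an exercise physiologist may lead training and also supervises the fitness tests.
- Section 6.2.1: weekly team meetings discuss participant progress.
- Section 8.1 (Activity Monitoring): the wrist device model differs by arm and is worn throughout, so it can reveal allocation at a visit.

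These passages are compatible with a coach scoring their own participant, and no passage forbids it. None assigns the two tasks to the same individual.

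**3. Illustration of size**

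Inputs: 23 per arm (46 randomized 1:1, synopsis), two-sided 5% level (section 9.4.9). Assumption with no source in the documents: measurement bias shifts the arm difference by b = 0.1, 0.2 or 0.3 SD, with no true effect.

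- Standard error of a standardised difference: sqrt(2/23) = 0.295.
- Shift in standard errors: k = b/0.295 = 0.34, 0.68, 1.02.
- Error rate: P(Z > 1.96 − k) + P(Z < −1.96 − k) = 6.3%, 10.4%, 17.4%.
- The same calculation with a noncentral t on 44 degrees of freedom gives 6.3%, 10.2%, 16.9%.

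This is an unadjusted comparison at one visit with no dropout. The planned model is a random-intercept mixed model, adjusted for baseline where necessary. Baseline adjustment would shrink the standard error, so a given bias would weigh more; dropout would work the other way.

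**The case against.** Much can be said for the plan. Section 6.3 openly states that coaches and participants are unblinded, and it claims to minimize bias, not to eliminate it. Section 9.4.9 labels the exploratory analyses hypothesis-generating. Several Aim 2 measures are instrument-read: body composition by bioimpedance, weight, finger-stick glucose and lipids, automated heart rate and blood pressure. Staff take a skill test of inter-tester agreement, gait is walked twice, and grip is repeated three times per hand. The exercise physiologist at the fitness tests is there for safety and technique; the text does not say that this person scores.

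These points limit the concern but do not answer it. Repetition and inter-tester agreement reduce random error and differences between testers; they do not prevent a tester from treating the arms differently. Hypothesis-generating status lowers the stakes, but the estimates will still be reported and used.

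A reader might infer that unblinded coaches and trainers do collect these outcomes. The documents do not say so: the evidence is shared role names and joint training. Nor is a trainer who tests their own participant a source of bias between arms by that fact alone, because both arms receive supervised training and participants are allocated to trainers at random (section 6.1.1). The arm-specific route is the Companion coach. A reader might also infer that everything in Aim 2 beyond blood chemistry is subjective; the instrument-read measures above show otherwise.

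**Conclusion.** The objectivity statement in 6.3 is wrong as written for about half of the listed Aim 2 endpoints, and the plan is silent on assessor blinding and on separating coaching from scoring. This part rests on the text alone.

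That bias would probably favour Companion is a judgement, based on the coach route and on participant expectation. Its size is unknown, and the error rates above show sensitivity, not an estimate. Whether any coach will in fact score their own participant cannot be settled from the documents.

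The effect is confined to the exploratory performance tests and questionnaires. The primary physical activity and sedentary outcomes come from accelerometry and are outside this point. The correction should be made because it changes what Aim 2 can support, but it does not threaten the main result.

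**What to change.** In section 6.3, limit the objectivity statement to accelerometry and instrument-read measures (bioimpedance, weight, finger-stick chemistry). Add that the performance tests and questionnaires are open to assessor or participant bias, and that Aim 2 results on them will be interpreted accordingly.

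In section 8.1, require that the person who times, counts and encourages at months 4 and 6 has not coached that participant through Companion and, where feasible, is not told the arm. Use staff already trained in measurement. Use one fixed encouragement script in both arms.

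The cost is less scheduling flexibility and a weaker bias-control statement. The documents give no staff numbers, so the team must confirm that the rota is workable; if it is not, the change to 6.3 should still be made. The rota does not remove participant bias in the self-completed questionnaires or in effort. It also does not guarantee masking: measurements may be taken at home, treatment-arm data hubs may be installed there until month 6, and weekly meetings discuss participants' progress.
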